	
 • AE review (Visits 2–11). • Physical examination (including weight) (Visits 5, 7 and 9). • Height (Visit 9). • ECG (Visits 5, 6, 7, 8 and 9). • Vital signs (Visits 2, 5, 6, 7, 8, 9 and 10). • Safety labs (hematology and biochemistry) (Visits 5, 6, 7 and 9; plus Visit 8 for patients taking concomitant valproic acid). • Urinalysis (Visit 9) • Serum IGF-1 levels (Visit 9). • Serum pregnancy test (if appropriate) (Visit 9). • PK blood samples: A blood sample for PK analysis of CBD and its main metabolites (as appropriate considering the patients weight [patient must weigh ≥ 12 kg]) will be taken as a trough sample at Visits 5, 6, 7, and 9 (PK sample must be trough at Visit 9 and preferentially trough at Visits 5, 6 and 7). The time of the patient's sample collection, time of latest IMP dose, time and type of meal consumed by the patient closest to the latest IMP dose will be recorded, as well as the time of latest concomitant medications. • Blood sample collection for the analysis of biomarkers (Visit 9). • Questionnaires: 
 ○ Visits 2, 5, 6, 7, 8 and 9: RSBQ, CGI-S and CGI-I (except Visit 2 for CGI-I), Hospital Services Use Questionnaire, and CSHQ. ○ Visits 2, 7 and 9: MBA-9. ○ Visits 2 and 9: Caregiver QoL questionnaire (SF-36) and Patient QoL questionnaire (CHQ-PF50). ○ Visits 5, 6, 7, 8, 9 and 10: Suicidality assessment. • The weekly symptom diary is to be completed by the caregiver weekly throughout the trial and reviewed at Visits 2, 3, 4, 5, 6, 7, 8 and 9. • The daily dosing diary is to be completed by the caregiver daily throughout the trial and reviewed at Visits 3, 4, 5, 6, 7, 8, 9 and 10. • Tanner Staging (for patients aged ≥ 7 years, or earlier if clinically indicated by onset of menarche or other signs of precocious puberty) (Visit 9). • Menstruation cycle review (Visits 2 and 9).
--	--

Study Code: GWND18064

EudraCT Number: 2018-003370-27

Clinical Protocol 4.1, 07Jul2020 (duplicate synopsis removed)

	
 • IMP dispensing (Visits 2, 5, 6, 7, 8 and 9); all caregivers will be provided with a dosing schedule. • IMP collection and compliance review (Visits 5, 6, 7, 8, 9 and 10).

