6.2 Exclusion Criteria

The patient may not enter the trial if ANY of the following apply:

- 6.2.1 Patient meets exclusion criteria for RTT diagnosis (traumatic brain injury, neurometabolic disease, or severe infection that causes neurological problems; grossly abnormal psychomotor development in the first 6 months of life).
- 6.2.2 Patient has clinically significant abnormal laboratory values, in the investigator's opinion.
- 6.2.3 Patient experiences more than weekly seizures (based on history over the last 2 months prior to screening) i.e., CSS 'epilepsy/seizure' score of 4 or 5.
- 6.2.4 Patient is taking more than 2 concurrent AEDs.
- 6.2.5 Any history of suicidal behavior or any suicidal ideation in the last month or at screening.
- 6.2.6 Patient has clinically relevant abnormalities in the ECG measured at screening or randomization (including QT interval, corrected by Bazett's correction formula [QTcB] interval > 450 msec, average of 3 measurements).
- 6.2.7 Patient has any concurrent cardiovascular conditions which will, in the investigator's opinion, interfere with the ability to assess the patient's ECGs or put the patient at risk because of participation in the trial.
- 6.2.8 Patient's first or second degree relative has a history of significant ECG abnormalities, in the opinion of the investigator (e.g., premature cardiac arrest, sudden death).
- 6.2.9 Patient has any known or suspected hypersensitivity to cannabinoids or any of the excipients of the IMP (active or placebo), such as sesame oil.
- 6.2.10 Patient has moderately impaired hepatic function at screening, defined as serum ALT or AST $> 3 \times$ ULN **or** total bilirubin [TBL] $> 2 \times$ ULN.

Study Code: GWND18064

EudraCT Number: 2018-003370-27

Clinical Protocol 4.1, 07Jul2020 (duplicate synopsis removed)

6.2.11 Female patient is of childbearing potential, unless willing to ensure that they or their partner use a highly effective method of birth control (e.g., combined [estrogen and progestogen containing], hormonal contraception^a associated with inhibition of ovulation [oral, intravaginal or transdermal], progestogen-only hormonal contraception^b associated with inhibition of ovulation [oral, injectable or implantable]^b, intrauterine devices/hormone-releasing systems^b, bilateral tubal occlusion^b, vasectomized partner^{b,c}, sexual abstinence^d) during the trial and for 3 months thereafter.

6.2.12 Female patient is pregnant (positive pregnancy test) or lactating.

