9.1.1 Clinic Visits

9.1.1.1 Visit 1 (Day -28, Screening)

The caregiver will complete the RSBQ (following documented training on how to complete the questionnaire).

The following assessments will be performed: demographics (including *MECP2* mutation), review of medical history and concomitant medications, vital signs, physical examination (including body weight), height, ECG and visit procedure related AEs.

The physician will complete the CSS.

Clinical laboratory samples (urine [where possible] and blood) will be taken for:

- Hematology.
- Biochemistry.
- Urinalysis (provided urine can be obtained).
- Pregnancy test (using a serum sample, as appropriate [[Section 9.2.2](#)]).
- THC screen (serum/urine)

May be carried out at the site using a THC urine dipstick; otherwise a urine or blood sample may be sent to the central laboratory. Patients weighing < 12 kg must not provide a serum sample for THC screen at Visit 1; if there are difficulties obtaining sufficient urine for THC testing at Visit 1, then a blood or urine sample must be collected at the site on another day within ± 7 days of Visit 1.

- Determination of serum IGF-1 levels.
- Biomarker analysis (if appropriate considering the patients' weight [patient must weigh \geq 16 kg] - [Section 9.2.13](#)).

A positive *MECP2* pathogenic mutation result is required to confirm eligibility at Visit 2. For those patients who do not have a known/documentated *MECP2* mutation, a blood sample will also be taken to confirm *MECP2* genetic mutation status. In cases where patient weight (< 19 kg) prevents the collection of a blood sample at Visit 1 for *MECP2* mutation analysis (where required), in addition to other scheduled samples as listed above, a blood sample for *MECP2* mutation analysis must be collected in advance of

Study Code: GWND18064

EudraCT Number: 2018-003370-27

Clinical Protocol 4.1, 07Jul2020 (duplicate synopsis removed)

Visit 1 (following informed consent [and where applicable, patient assent] as per [Section 9.2.1](#)).

In all instances, the collection of blood samples for hematology, biochemistry, and pregnancy test (as appropriate) should take place at Visit 1.

The patient screening visit will be registered in the eCRF and a patient number will be issued. Patients who satisfy all inclusion and none of the exclusion criteria specified in [Section 6](#) will then begin the 14 to 28-day baseline period.

The investigator will complete the suicidality assessment.

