There are certain days/periods where she performs much worse than usual.

16.	0	1	2
-----	---	---	---

There are times when she appears miserable for no apparent reason.

17.	0	1	2
-----	---	---	---

Seems to look through people into the distance.

18.	0	1	2
-----	---	---	---

Does not use hands for purposeful grasping.

© Rebecca H. Mount, Richard P. Hastings, Sheena Reilly, Hilary Cass, 1998

SPONSOR: GW RESEARCH LIMITED

Study Code: GWND18064
EudraCT Number: 2018-003370-27
Clinical Protocol 4.1, 07Jul2020 (duplicate synopsis removed)

19.	

0	1	2	

	0	1	2	Swallows air.
0	1	2			
20.	

0	1	2	

	0	1	2	Hand movements are uniform and monotonous.
0	1	2			
21.	

0	1	2	

	0	1	2	Has frequent naps during the day.
0	1	2			
22.	

0	1	2	

	0	1	2	Screams hysterically for long periods of time and cannot be consoled.
0	1	2			
23.	

0	1	2	

	0	1	2	Although can stand independently tends to lean on objects or people.
0	1	2			
24.	

0	1	2	

	0	1	2	Restricted repertoire of hand movement.
0	1	2			
25.	

0	1	2	

	0	1	2	Abdomen fills with air and sometimes feels hard.
0	1	2			
26.	

0	1	2	

	0	1	2	Spells of laughter for no apparent reason during the day.
0	1	2			
27.	

0	1	2	

	0	1	2	Has wounds on hands as a result of repetitive hand movements.
0	1	2			
28.	

0	1	2	

	0	1	2	Makes mouth grimaces.
0	1	2			
29.	

0	1	2	

	0	1	2	There are times when she is irritable for no apparent reason.
0	1	2			
30.	

0	1	2	

	0	1	2	Spells of inconsolable crying for no apparent reason during the day.
0	1	2			
31.	

0	1	2	

	0	1	2	Uses eye gaze to convey feelings, needs and wishes.
0	1	2			
32.	

0	1	2	

	0	1	2	Makes repetitive tongue movements.
0	1	2			

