Appendix 3.9 Suicidality Assessment

An example of the suicidality assessment is shown below:

- *Has the child expressed any wish to be dead?*
- *Has the child made any suicide attempts?*
- *Has the child harmed themselves in any way or shown any non-suicidal self-injurious behavior?*

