### **9.3.4 Suicidality Assessment**

The profound cognitive impairment of RTT patients is such that the Children's Columbia-Suicide Severity Rating Scale is not considered appropriate in this trial. Instead, suicidality will be assessed by the investigator via a clinical interview with the caregiver.

Responses to the suicidality assessment will be summarized by visit and treatment group.

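### The suicidality form states no recall window and SAP 9.3.4 plans no comparison with Visit 1, so the planned table cannot separate long-standing from new self-injury

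*Protocol*

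**What the plan says.** Protocol Appendix 3.9 introduces the form with the words "An example of the suicidality assessment is shown below" and lists three questions. They cover a wish to be dead, suicide attempts ("Has the child made any suicide attempts") and self-harm ("Has the child harmed themselves in any way or shown any non-suicidal self-injurious behavior"). None has a time frame. Section 9.2.17.9 sets the mode, an investigator interview with the caregiver, but no window either.

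The form is used at screening (section 9.1.1.1: "The investigator will complete the suicidality assessment") and six times afterwards (synopsis: "Visits 5, 6, 7, 8, 9 and 10: Suicidality assessment"). Only one version is shown.

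Exclusion 6.2.5 reads "Any history of suicidal behavior or any suicidal ideation in the last month or at screening". It does not mention non-suicidal self-injury.

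Suicidality is a named safety endpoint in Protocol 4.1.2 and SAP 2.2.2. Protocol 13.6.3.5.1 says only that responses are summarized and listed as appropriate. SAP 9.3.4 plans one analysis: "Responses to the suicidality assessment will be summarized by visit and treatment group".

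**The concern.** A safety table should help the reader see what began after dosing. An undated question repeated seven times does that only if each answer is set against the pre-dose answer, and SAP 9.3.4 does not do this.

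The self-injury item is the most exposed. The protocol treats hand injury from stereotypies as a feature of the disease, since RSBQ item 27 rates "Has wounds on hands as a result of repetitive hand movements". If caregivers or investigators also count such injury on the suicidality form, some patients will answer Yes before any drug is given. Later Yes counts then mix a standing trait with new behavior. A real difference between arms is diluted, and a chance imbalance in the trait at screening could look like a drug effect.

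The trial was discontinued and its analysis is purely descriptive (SAP 1, 8 and 9.5). No test or model will correct for this, so readers rely on the choice of table.

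**Working it through.** The plan gives no figure on this point, so there is none to reproduce. The check has two parts.

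**Reading the documents side by side**

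- *Recall window.* Other forms in the protocol state one. The Hospital Services Use Questionnaire (Appendix 3.8) has separate baseline and since-last-visit versions, the CSHQ refers to the past week, and the RSBQ asks about the present. Appendix 3.9 has nothing comparable.
- *Use of baseline.* SAP 6.1.2 defines the safety baseline as the last pre-dose value. For this form that is Visit 1, as it is not scheduled at Visit 2. The SAP uses baseline for treatment-emergent ALT and AST (9.2.1), vital sign changes (9.3.1) and Tanner shifts (9.3.5), but not in 9.3.4.
- *Item 1 (wish to be dead).* Ideation more than a month before screening is not excluded, so carry-over is possible. It is probably rare, given the cognitive impairment described in Protocol 9.2.17.9.
- *Item 2 (attempts).* Any history of suicidal behavior is excluded. A Yes after entry should therefore be new in a correctly enrolled patient.
- *Item 3 (self-injury).* Earlier non-suicidal self-injury is not excluded, so carry-over is open.
- *Possible readings.* If the item is read as 'ever', a Yes at screening persists. If it is read as 'now', ongoing self-injury is still Yes at each visit. Either way the by-visit count mixes old and new.

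**Illustration under the 'ever' reading**

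Let p be the share with Yes at Visit 1, taken as equal in both arms, and q the risk of a new episode on treatment, taken as unrelated to the Visit 1 answer. The documents give neither, so both are assumed: q = 10% on active, 5% on placebo.

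Yes share by end of treatment = p + (1 − p)q

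Difference between arms = (1 − p)(q active − q placebo)

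| Assumed p | Active | Placebo | Difference |
|---|---|---|---|
| 0% | 10.0% | 5.0% | 5.0 points |
| 10% | 10 + 90 × 0.10 = 19.0% | 10 + 90 × 0.05 = 14.5% | 4.5 points |
| 25% | 25 + 75 × 0.10 = 32.5% | 25 + 75 × 0.05 = 28.75% | 3.75 points |
| 50% | 50 + 50 × 0.10 = 55.0% | 50 + 50 × 0.05 = 52.5% | 2.5 points |

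The share of new episodes that leaves no trace in the Yes count equals p. At the planned 84 patients per comparison group (pooled placebo 42 + 42), the expected number of active patients with a new episode is 84 × 0.10 = 8.4. Of these, 84 × (1 − p) × 0.10 = 7.6, 6.3 or 4.2 would show as a new Yes at p = 10%, 25% or 50%.

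**What a new-onset count gives**

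Among patients with No at Visit 1, the share with a later Yes is (1 − p)q ÷ (1 − p) = q. At p = 25%, 84 × 0.75 = 63 patients per group had No. The new Yes counts are 6.3 and 3.15, or 10% and 5%, so the 5.0 points return. Episodes in patients already Yes (84 × 0.25 × 0.10 = 2.1 on active) stay hidden.

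**The case against.** A reader might infer that every patient with past self-injury will be counted as Yes at each visit and that new on-treatment events cannot be seen at all. The documents do not support either inference.

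- *Persistent Yes is not certain.* It follows for past self-injury only under an 'ever' reading. The form does not say that, and an investigator conducting an interview can apply a time frame. What the text establishes is ambiguity, with possible differences between raters and visits.
- *The form is an example.* The electronic version is not available here. The introduction to Appendix 3 says, however, that the appended forms show the content and that the format will differ. A recall window is content.
- *New events have other routes.* Listings run by patient and, where applicable, in time order (SAP 6), so a change from No to Yes can be traced. A new sign or a worsening after Visit 1 is an adverse event (Protocol 12.1.1, 12.6) and enters the treatment-emergent tables. This stands. But listings give no count by arm, adverse event reporting depends on the investigator's judgment, and the special-interest terms in SAP Appendix 2 concern abuse liability, with none for suicidal ideation, suicide attempt or self-injury.
- *Subtraction may suffice.* If the by-visit summary includes Visit 1, if Yes never reverts, and if no visit is missed, the later Yes share minus the Visit 1 share gives the new Yes share. At p = 25% this is 32.5 − 25 = 7.5 points, and 7.5 ÷ 75% = 10%. That is correct under those conditions. When answers change in both directions, the table shows only the net change. Missed visits also lower the later percentages, because SAP 4.1 generally takes all patients in the analysis set as denominator.
- *The overlap with stereotypies is not shown.* Nothing says that investigators record such hand wounds under item 3. RSBQ item 27 makes overlap plausible, no more.

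**Conclusion.** The point holds as a minor one. The form states no recall window, and SAP 9.3.4 sets no answer against Visit 1. The planned table by arm therefore cannot separate long-standing from new self-injury within patients. Nor can it count patients with any new on-treatment Yes when answers change between visits. Item 3 carries most of the problem, item 1 little, and item 2 is largely protected by exclusion 6.2.5.

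The size is not known. Under the 'ever' reading, a between-arm difference in new events shrinks by the factor 1 − p, so a tenth is lost at p = 10% and half at p = 50%. This rests on assumed p and q, equal p in the arms, and the planned group sizes, which a discontinued trial may not have reached. The table would still show part of a true difference, so it would be wrong to conclude that it can show nothing about the drug.

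**What to change.** In SAP 9.3.4, add one table by arm and item: the number of patients with No at Visit 1 and Yes at any later visit, with patients who had No at Visit 1 as denominator. Show self-injury apart from items 1 and 2. This works on data already collected. SAP 6.1.9 already allows further derived variables outside the primary and secondary endpoints to be documented in the programs. A footnote should say that new episodes in patients already Yes at Visit 1 are not captured.

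For any further use of the form, ask 'ever' and 'in the last month' separately at screening, and 'since the last study visit' afterwards. This cannot change answers already recorded in the discontinued trial.

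The cost is one extra table and a small form revision.

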Appendix 3.10 Children's Sleep Habits Questionnaire

An example of the CSHQ is shown below⁹.

Child's Sleep Habits (Preschool and School-Aged) (Abbreviated Version)				Coding		

The following statements are about your child's sleep habits and possible difficulties with sleep. Think about the past week in your child's life when answering the questions. If last week was unusual for a specific reason (such as your child had an ear infection and did not sleep well or the TV set was broken), choose the most recent typical week. Answer USUALLY if something occurs 5 or more times in a week; answer SOMETIMES if it occurs 2-4 times in a week; answer RARELY if something occurs never or 1 time during a week. Also, please indicate whether or not the sleep habit is a problem by circling "Yes," "No," or "Not applicable (N/A)".
						

Bedtime
 
Write in child's bedtime: _____
						
	3 Usually (5-7)	2 Sometimes (2-4)	1 Rarely (0-1)	Problem?		
1) Child goes to bed at the same time at night (R)				Yes	No	N/A
2) Child falls asleep within 20 minutes after going to bed (R)				Yes	No	N/A
3) Child falls asleep alone in own bed (R)				Yes	No	N/A
4) Child falls asleep in parent's or sibling's bed				Yes	No	N/A
5) Child needs parent in the room to fall asleep				Yes	No	N/A
6) Child struggles at bedtime (cries, refuses to stay in bed, etc.)				Yes	No	N/A
7) Child is afraid of sleeping in the dark				Yes	No	N/A
8) Child is afraid of sleep alone				Yes	No	N/A

Sleep Behavior
 
Child's usual amount of sleep each day: _____ hours and _____ minutes (combining nighttime sleep and naps)
						
	3 Usually (5-7)	2 Sometimes (2-4)	1 Rarely (0-1)	Problem?		
9) Child sleeps too little				Yes	No	N/A
10) Child sleeps the right amount (R)				Yes	No	N/A
11) Child sleeps about the same amount each day (R)				Yes	No	N/A
12) Child wets the bed at night				Yes	No	N/A
13) Child talks during sleep				Yes	No	N/A
14) Child is restless and moves a lot during sleep				Yes	No	N/A
15) Child sleepwalks during the night				Yes	No	N/A
16) Child moves to someone else's bed during the night (parent, brother, sister, etc.)				Yes	No	N/A
17) Child grinds teeth during sleep (your dentist may have told you this)				Yes	No	N/A
18) Child snores loudly				Yes	No	N/A

CSHQ Abbreviated

SPONSOR: GW RESEARCH LIMITED

Study Code: GWND18064
 EudraCT Number: 2018-003370-27
 Clinical Protocol 4.1, 07Jul2020 (duplicate synopsis removed)

Coding

Sleep Behavior (continued)

	3 Usually (5-7)	2 Sometimes (2-4)	1 Rarely (0-1)	Problem?		
19) Child seems to stop breathing during sleep				Yes	No	N/A
20) Child snores and/or gasps during sleep				Yes	No	N/A
21) Child has trouble sleeping away from home (visiting relatives, vacation)				Yes	No	N/A
22) Child awakens during night screaming, sweating, and inconsolable				Yes	No	N/A
23) Child awakens alarmed by a frightening dream				Yes	No	N/A

Waking During the Night

	3 Usually (5-7)	2 Sometimes (2-4)	1 Rarely (0-1)	Problem?		
24) Child awakes once during the night				Yes	No	N/A
25) Child awakes more than once during the night				Yes	No	N/A

Write the number of minutes a night waking usually lasts: _____

Morning Waking/Daytime Sleepiness

Write in the time of day child usually wakes in the morning: _____

	3 Usually (5-7)	2 Sometimes (2-4)	1 Rarely (0-1)	Problem?		
26) Child wakes up by him/herself (R)				Yes	No	N/A
27) Child wakes up in negative mood				Yes	No	N/A
28) Adults or siblings wake up child				Yes	No	N/A
29) Child has difficulty getting out of bed in the morning				Yes	No	N/A
30) Child takes a long time to become alert in the morning				Yes	No	N/A
31) Child seems tired				Yes	No	N/A

Child has appeared very sleepy or fallen asleep during the following (check all that apply):

	1 Not Sleepy	2 Very Sleepy	3 Falls Asleep
32) Watching TV			
33) Riding in car			

SPONSOR: GW RESEARCH LIMITED

Study Code: GWND18064
EudraCT Number: 2018-003370-27
Clinical Protocol 4.1, 07Jul2020 (duplicate synopsis removed)

Subscale Items Children's Sleep Habits Questionnaire (CSHQ)

Numbers in parentheses refer to CSHQ item number

1. Bedtime Resistance (6 items)

Goes to bed at same time (1) (R)^A
Falls asleep in own bed (3) (R)
Falls asleep in other's bed (4)
Needs parent in room to sleep (5)
Struggles at bedtime (6)
Afraid of sleeping alone (8)

2. Sleep Onset Delay (1 item)

Falls asleep in 20 minutes (2) (R)

3. Sleep Duration (3 items)

Sleeps too little (9)
Sleeps the right amount (10) (R)
Sleeps same amount each day (11) (R)

4. Sleep Anxiety (4 items)

Needs parent in room to sleep (5)
Afraid of sleeping in the dark (7)
Afraid of sleeping alone (8)
Trouble sleeping away (21)

5. Night Wakings (3 items)

Moves to other's bed in night (16)
Awakes once during night (24)
Awakes more than once (25)

6. Parasomnias (7 items)

Wets the bed at night (12)
Talks during sleep (13)
Restless and moves a lot (14)
Sleepwalks (15)
Grinds teeth during sleep (17)
Awakens screaming, sweating (22)
Alarmed by scary dream (23)

7. Sleep Disordered Breathing (3 items)

Snores loudly (18)
Stops breathing (19)
Snorts and gasps (20)

8. Daytime Sleepiness (8 items)

Wakes by himself (26) (R)
Wakes up in negative mood (27)
Others wake child (28)
Hard time getting out of bed (29)
Takes long time to be alert (30)
Seems tired (31)
Watching TV (32)
Riding in car (33)

Total Sleep Disturbance Score (33 items)^B

Scoring: Usually = 3 Sometimes = 2 Never/Rarely = 1

^A Note: Some items (R) should be reversed in scoring, so that a higher score reflects more disturbed sleep behavior.

^B Note: The Total Sleep Disturbance Score: Consists of all 33 subscale items instead of 35 (although items 5 and 8 are on both the Bedtime Resistance and Sleep Anxiety scales, they should be included only once in the total score)

Study Code: GWND18064
EudraCT Number: 2018-003370-27
Clinical Protocol 4.1, 07Jul2020 (duplicate synopsis removed)

